7.1.2.11 PATIENT'S SATISFACTION WITH DRUG TREATMENT

Patient's overall satisfaction with treatment is assessed via a 5-point likert question (extremely dissatisfied, dissatisfied, neither satisfied nor dissatisfied, satisfied and extremely satisfied).

At each visit, Visit X, overall satisfaction will be presented only for those who remained on tofacitinib at the last visit, Visit X-1. This will be split by those who stop taking tofacitinib at Visit X and those that remain on tofacitinib at Visit X.

7.2 SAFETY ENDPOINTS

Incidence and severity of all adverse events including serious adverse events (SAEs).

The reporting of safety data will be in accordance with Pfizer Data Standards.

7.3 COVARIATES, FACTORS AND POTENTIAL CONFOUNDERS

7.3.1 FACTORS OF INTEREST FOR PRIMARY ANALYSIS

The following covariates will be included in the primary analysis:

- a. DAS 28-4 (ESR) LDA (see sections 6.1.2.4.1 and 6.1.2.2.3 for derivations) [Note: this is a binary endpoint].
- b. Indicator variable for whether patient has achieved change from baseline of DAS28-4 (ESR) > 1.8 (see section 6.1.2.4.1 for derivations of DAS28-4 (ESR)) [Note: this is a binary endpoint].

Change from baseline will be calculated as:

$\Delta\text{DAS28-4 (ESR)} = \text{DAS28-4 (ESR) at time point} - \text{DAS28-4 (ESR) at baseline}$

If a patient has achieved $\Delta\text{DAS28-4 (ESR)} > 1.8$ the indicator will be 1,

If $\Delta\text{DAS28-4 (ESR)} > 1.8$ is not achieved, the indicator will be 0.

- c. Physician Global Assessment of Arthritis – measured on a visual analogue scale (0-100mm).
- d. Patient's Global Assessment of Arthritis – measured on a visual analogue scale (0-100mm).
- e. Patient's Assessment of Arthritis Pain – measured on a visual analogue scale (0-100mm).
- f. Patient's overall satisfaction with treatment:

For each patient the response to the question ‘How satisfied are you with the drugs that you have received for your arthritis since your last visit?’ will be assigned as below:

0 = extremely dissatisfied,

1 = dissatisfied,

2 = neither satisfied nor dissatisfied,

3 = satisfied

4 = extremely satisfied

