7.7. Study size

The analysis of the primary endpoint is a time to event analysis, where the event is treatment escalation. It is possible for multiple events to occur for each patient within the follow-up period. The primary analysis aims to investigate which of the factors listed actually affect the rate at which a patient's treatment is changed. In order to determine an appropriate sample size for this study recurrent event data was simulated, using the methods described by Jahn-Eimermacher *et al.* (2015), and analysed using cox proportional-hazards models.[21]

The distribution of each of the factors was obtained from the ORAL STANDARD study:

Achieve DAS28 < 3.2	-	Binomial(n, 0.2)
Achieve Δ DAS28 > 1.8	-	Binomial(n, 0.6)
Δ Patient Global Assessment	-	Normal(-29.31, 38.579 ²)
Δ Physician Global Assessment	-	Normal(-27.01, 30.966 ²)
Δ Pain score	-	Normal(-34.99, 24.672 ²)

The baseline hazard rate was assumed to be 3.16 events per patient over the follow-up period.

The impact of each the factors on the hazard rate, (entered as the regression coefficient), is used to simulate the event times for each patient given their values for the simulated factors. The regression coefficients were assumed to be (-0.288, -2.303, -0.01, -0.01, -0.01). Simulations were carried out for sample sizes ranging from 100 to 4,500.

Figure 2 shows the power to detect an effect of each factor against sample size for the 5 different factors.

[figure not shown]

Figure 2: Plot of Power against Sample Size for simulations of recurrent event data analysed using cox-proportional hazards model including all 5 factors of interest.

Given the initial assumptions the power to detect an impact of 4 of the 5 factors, within the full cox proportional hazards model was greater than 80% with a sample size of 1000 patients. The power to detect an effect of the remaining factor, achieving $DAS28 \leq 3.2$, was around 50% for 1500 patients and 60% for 2000 patients. The power is very high for $\Delta DAS28 > 1.8$, mainly due to the high proportion of patients assumed to achieve the criteria and the high impact achieving the criteria is assumed to have on the rate of treatment escalation (significantly reducing it).

Sensitivity analyses were carried out around the assumptions made for the simulations. Full details of the sensitivity analyses will be included in the SAP.

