7.9.2. Efficacy Analysis

7.9.2.1. Primary analysis

The primary analysis will investigate the impact of various factors on the rate of treatment escalation. Cox proportional-hazards modelling will be used, with status of each patient (whether they experienced a treatment escalation or not) and the times of such treatment escalations being used for the baseline model.

The factors that will be investigated and thus included in the model will be:

- whether or not a patient achieves LDA, as defined by DAS28-4 (ESR) ≤ 3.2 .
- whether or not a patient achieves change from baseline in DAS28-4 (ESR) > 1.8
- Patient's Global Assessment of Arthritis
- Physician Global Assessment of Arthritis
- Patient's Assessment of Arthritis Pain
- Patient's satisfaction with drug treatment

If patients withdraw or are lost to follow-up they will be censored at the time of the last available visit.

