7.1.2.4 CHANGE FROM BASELINE IN DAS28-4 (ESR) AND DAS28-4 (CRP)

7.1.2.4.1 DAS28-4

$\text{DAS28-4 (ESR)} = 0.56*\sqrt{(\text{TJC28})} + 0.28*\sqrt{(\text{SJC28})} + 0.70*\ln(\text{ESR in mm/ hour}) + 0.014*\text{PtGA in mm.}$

DAS28-4 (CRP) is similarly calculated by:

$\text{DAS28-4 (CRP)} = 0.56*\sqrt{(\text{TJC28})} + 0.28*\sqrt{(\text{SJC28})} + 0.36*\ln(\text{CRP in mg/l} + 1) + 0.014*\text{PtGA in mm} + 0.96$

Where TJC28 is the Tender Joint Count, SJC28 is the Swollen Joint Count, CRP is the C-reactive protein in mg/L, ESR is the Erythrocyte Sedimentation Rate in mm/first hour and

PtGA is the Patient's Global Assessment of Health in mm. PtGA will be used in this calculation.

The change from baseline in DAS28-4 (ESR) will be calculated at each time point as:

DAS28-4 (ESR) at time point – DAS28-4 (ESR) at baseline.

Similarly change from baseline in DAS28-4 (CRP) will be calculated at each time point as:

DAS28-4 (CRP) at time point – DAS28-4 (CRP) at baseline.

Change from Baseline in DAS 28-4 at all time points (M3, M6, M9, M12, M15, M18, M21, M24) will be presented.

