9.1.1 ANALYSIS FOR RECURRENT EVENT DATA

In order to account for the possibility that there are multiple events occurring for each patient cox-proportional hazards modeling will be used with adjustment for recurrent events. This involves fitting either the Andersen and Gill or Prentice, Williams and Peterson gap-time models to the data.

For each patient, the data will be split into time periods, then data for each time window should include the patient's status, the time of event (if the event occurred) and the value of each of the factors of interest:

So, for patient A, who had events at M6 and M18, their data could look like this:

Patient	Start	Stop	Treatment Escalation Status	Factor A	Factor B	Factor C
A	0	M6	1	3.9	0.6	-10
A	M6	M12	0	3.0	1.5	-20
A	M12	M8	1	2.8	1.7	-10
A	M18	M24	0	2.2	2.3	-10

The cox proportional hazards model (using PROC PHREG) is then used, including the factors of interest (Section 7.3.1) to determine which, if any of them, have an impact on the rate at which treatment changes occur.

Any potential confounders should be included in the model also (Section 7.3.3).

The estimated event rate will be presented, along with 95% confidence interval and p-value, for each of the covariates of interest. Note: These will not be presented for the variables considered to be confounders.

The number and proportion of people experiencing an event at each time point will be presented.

Supportive tables will also be presented which summarises each of the covariates in the model at each visit.

The analysis will be performed for each type of escalation as defined in section 7.1.1 and overall.

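### The primary-model indicator for a DAS28 change above 1.8 is coded as time point minus baseline, so it flags worsening and scores every responder 0

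*SAP*

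**What the plan says.** SAP 7.3.1(b) lists as a primary factor an "Indicator variable for whether patient has achieved change from baseline of DAS28-4 (ESR) > 1.8". Beneath it the SAP gives the subtraction, value at the time point minus value at baseline. It assigns 1 if the result is above 1.8 and 0 if not. There is no absolute value and no word giving a direction of benefit.

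SAP 7.1.2.4.1 uses the same subtraction for the secondary endpoint: "DAS28-4 (ESR) at time point – DAS28-4 (ESR) at baseline".

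The Protocol, section 7.9.2.1, names the factor as "whether or not a patient achieves change from baseline in DAS28-4 (ESR) > 1.8" and does not say which value is subtracted from which. The factor above it in the same list is "whether or not a patient achieves LDA, as defined by DAS28-4 (ESR) ≤ 3.2", so a low score is the good result.

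Protocol 7.7 plans the study with 60% of patients meeting the change criterion and a regression coefficient of -2.303. It calls the power for this factor very high, "mainly due to the high proportion of patients assumed to achieve the criteria" and because meeting the criterion is assumed to reduce escalation strongly.

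The summary table in SAP 9.2.6 repeats the criterion, with the same sign, for the main FAS and PPAS analyses and for both prior-visit analyses.

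**The concern.** With time point minus baseline, improvement is a negative number. A threshold of above +1.8 then selects patients whose disease activity has risen substantially. A patient who falls from 6.0 to 3.0 has a change of -3.0 and scores 0, the same as a patient who has not changed.

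This is one of the six primary factors and the one with the largest planned effect. SAP 9.1.1 reports an estimate, a 95% confidence interval and a p-value for it, overall and for each escalation type. If programmed as written, the result under this label would compare severe worsening with everything else. It would not compare response with non-response, and it would rest on very few patients.

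**Working it through.** **1. The plan's own figure.** Protocol 7.7 states power above 80% at 1000 patients for this factor, with prevalence 0.6 and coefficient -2.303. The hazard ratio is exp(-2.303) = 0.10. Recurrent events were simulated with the protocol's five distributions and coefficients. The simulation assumed a constant hazard of 3.16 events per patient, complete follow-up, an Andersen-Gill Cox model, two-sided 5% (the alpha is assumed, as none is stated) and 400 runs per setting. Power for this factor was 100% at 1000, 1500 and 2000 patients. For this factor the planning statement therefore reproduces, provided that the indicator means improvement in 60% of patients.

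**2. Direction, from the text.**

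| Source | Content | Direction |
|---|---|---|
| SAP 7.3.1(b) | time point minus baseline, flag if > 1.8 | worsening |
| SAP 7.1.2.4.1 | time point minus baseline | improvement is negative |
| Protocol 7.9.2.1 | achieves a change > 1.8 | not defined |
| Protocol 7.7 | 60% meet it, coefficient -2.303 | improvement |

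Neither document contains a statement that corrects the sign.

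**3. The SAP's data-layout example (9.1.1).** It is introduced with "So, for patient A, who had events at M6 and M18, their data could look like this". Factor A is 3.9, 3.0, 2.8, 2.2 and Factor B is 0.6, 1.5, 1.7, 2.3. The row sums are 3.9 + 0.6 = 3.0 + 1.5 = 2.8 + 1.7 = 2.2 + 2.3 = 4.5. The columns are not labelled. If they are DAS28 and its change, the baseline is 4.5 and Factor B is baseline minus current. Under that reading:

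| Row | DAS28 | Change per SAP 7.3.1 | Indicator as written | Indicator for improvement > 1.8 |
|---|---|---|---|---|
| 1 | 3.9 | -0.6 | 0 | 0 |
| 2 | 3.0 | -1.5 | 0 | 0 |
| 3 | 2.8 | -1.7 | 0 | 0 |
| 4 | 2.2 | -2.3 | 0 | 1 |

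**4. How rare the written flag would be.** Inputs: P(improvement > 1.8) = 0.60 and 1500 patients, both from Protocol 7.7. The normal shape and the SD of the change, s, are assumptions. With z(0.6) = 0.2533, the mean change is -(1.8 + 0.2533s). Then P(change > +1.8) = 1 - Φ[(1.8 + 1.8 + 0.2533s)/s] = 1 - Φ(3.6/s + 0.2533).

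| s | Mean change | 3.6/s + 0.2533 | P(flag = 1) at one visit | Of 1500 |
|---|---|---|---|---|
| 1.0 | -2.05 | 3.853 | 0.00006 | 0.1 |
| 1.4 | -2.15 | 2.825 | 0.0024 | 3.6 |
| 1.6 | -2.21 | 2.503 | 0.0062 | 9.2 |
| 2.0 | -2.31 | 2.053 | 0.0200 | 30 |

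The planned number is 0.60 × 1500 = 900.

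**5. What the coefficient would show.** Suppose that responders truly have a hazard ratio of 0.10 and nothing else differs. Flagged patients are all non-responders, with relative hazard 1. The rest average (0.6 × 0.1 + (0.4 - p) × 1)/(1 - p), where p is the flagged proportion. For p near 0 this is 0.46, an apparent hazard ratio of 1/0.46 = 2.17. For p = 0.02 it is 0.44/0.98 = 0.449, a ratio of 2.23. The planned value is 0.10.

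**6. Conflict with the LDA factor.** A patient with DAS28 at or below 3.2 can score 1 under the written rule only if baseline was below 3.2 - 1.8 = 1.4. SAP 3.2 describes patients starting treatment for moderate to severely active disease, so the two indicators could hardly ever both be 1.

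**The case against.** The sign contradiction itself is not open to dispute. The case on the other side concerns its consequences, and several parts of it stand.

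- **Other factors remain.** LDA, both global assessments, pain and satisfaction stay in the primary model, so adjustment for disease status is not lost. What is lost is the one binary term for change.
- **The sensitivity model is sound.** SAP 7.3.2 uses continuous DAS28 and its continuous change, in FAS and PPAS. The sign convention does not alter the information there, provided that the coefficient is read correctly. It is a sensitivity analysis, however, and does not replace the primary factor.
- **The error might be caught.** SAP 9.2.2 summarises every model factor by time point, and an indicator near 0 to 2% would look odd against a planned 60%. A programmer might also infer the intended direction from the wording. Both are likely, but neither is assured, and the written formula is explicit.
- **The example table is only suggestive.** Its columns are unlabelled, Factors A and B are continuous whereas the primary DAS28 factors are binary, and Factor C is negative. The conclusion does not depend on this table.
- **The count of 0 to 30 applies to one visit.** The factor varies over time, with up to eight post-baseline visits. Under the same normal model, with an assumed within-patient correlation of 0.3 to 0.7, patients ever flagged would number below 1 (SD 1.0) to about 120 to 190 (SD 2.0) of 1500. The flag remains rare at each visit.
- **The hazard ratio does not simply invert.** Severe worsening against all others is a different contrast, and with almost no flagged patients it may not be estimable.

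**Conclusion.** The concern holds. As written, SAP 7.3.1(b) flags a rise in DAS28 of more than 1.8, whereas Protocol 7.7 planned a factor for improvement of that size. This follows from the text alone and needs no assumption.

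The size does rest on assumptions: a normal change with SD 1.0 to 2.0, calibrated to the planned 60%. On that basis about 0 to 30 of 1500 patients would be flagged at a given visit, against about 900. The apparent hazard ratio would be about 2.2, imprecise or inestimable, where 0.10 was planned. The conclusion is the same across the whole SD range. The damage is confined to the binary change factor, in every analysis that uses it. The error must be corrected before the final model is run.

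**What to change.** In SAP 7.3.1(b), define the indicator as 1 if DAS28-4 (ESR) at baseline minus DAS28-4 (ESR) at the time point is greater than 1.8 (equivalently, change from baseline below -1.8), and 0 otherwise. Carry the same wording into the four rows of the SAP 9.2.6 table that use the criterion. In 7.3.2(b), state that a negative continuous change means improvement, so that the coefficient is read correctly. SAP 7.1.2.4.1 is ordinary change-from-baseline arithmetic and can stay as it is.

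In Protocol 7.9.2.1, replacing change with improvement would remove the ambiguity. That section does not itself carry the error, so the rewording is a useful clarification that could go into any later amendment.

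The cost is a short SAP correction and one line of code, plus the protocol wording if it is taken up. No new data are needed. SAP 4.1 limits the first interim analysis to secondary endpoints, excludes modelling from the second, and has the third follow the second, so no planned interim model result is affected.

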7.3.2 FACTORS OF INTEREST FOR SENSITIVITY OF THE PRIMARY ANALYSIS

The following covariates will be included in a sensitivity analysis of the primary endpoint:

- a. DAS28-4 with Erythrocyte Sedimentation Rate (ESR) (section 7.1.2.4.1).
[Note: this is a continuous endpoint].
- b. Δ DAS28-4 (ESR), [Note: this is a continuous endpoint].
- c. Physician Global Assessment of Arthritis
- d. Patient’s Global Assessment of Arthritis
- e. Patient’s Assessment of Arthritis Pain
- f. Patient’s overall satisfaction with treatment
- g. Incidence of comorbidities
 - 1 if patient has at least one comorbidity
 - 0 if no comorbidities are recorded

7.3.3 POTENTIAL CONFOUNDERS TO BE INCLUDED IN THE PRIMARY ANALYSIS

A number of potential confounders will also be included in the primary analysis and all sensitivity analyses:

- Age at baseline
- Gender
- Duration of disease at baseline
- Indicator of tofacitinib dose
 - 1 if recommended dose of 5mg per day (i.e. TofInterval = BID),
 - 0 if reduced dose of 2.5mg per day (i.e. TofInterval = Daily).
- Poor prognostic factors (PF) indicator (1 if at least one Poor PF is present, 0 otherwise)
- Indicator of dose of MTX or combination partner (1 if increase in dose since last visit, 0 otherwise)
- Indicator of dose of Glucocorticoids (1 if increase in dose since last visit, 0 otherwise)
- Whether patient on 2nd or 3rd line treatment (see below)

A patient is defined as on 2nd line treatment if they were prescribed only csDMARDs prior to enrolling in the study.

A patient is defined as on 3rd line treatment if they were prescribed bDMARDs prior to enrolling in the study.

For a list of the medications considered to be csDMARDs and bDMARDs please see the eCRF.

- Indicator of tolerability issues (1 if treatment termination due to tolerability issues, 0 otherwise).
- Indicator of efficacy issues (1 if treatment termination due to efficacy issues, 0 otherwise).
- Incidence of the following comorbidities documented at the baseline visit (a term will be fitted for each comorbidity with the value 1 if the comorbidity is recorded for a patient or 0 otherwise):
 - Ischemic cardiovascular disease
 - Malignancies
 - Infections
 - Gastro disease
 - Osteoporosis
 - Depression

Any other variables observed to be potential confounders will also be investigated.

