Despite insufficient response after 3 to 6 months therapy, treat-to-target recommendations of EULAR were only applied in 50% of the German course and prognosis of early arthritis cohort (CAPEA).[14] In an analysis of a cohort from the “Kerndokumentation”, a national database of the German Collaborative Arthritis Centres, 45% of patients were not within DAS28 low disease activity range and therefore would have needed adaption of therapy according to current treatment guidelines. In contrast, rheumatologists’ global assessment of disease activity differed, 80% perceived their patients to be in the low disease activity range and, hence, as being adequately treated.[15]

These observations suggest that in a real-world setting, criteria other than calculated DAS28 remission or low disease activity alone may guide treatment decisions. Among such criteria, satisfaction with drug treatment is of particular interest. On the one hand, a patient who is content with his current therapy is less likely to be willing to change a therapy solely to achieve a better DAS28 score. On the other hand, patient preference and satisfaction of a therapy strongly affects adherence to a prescribed medication, ultimately affecting treatment outcome and efficacy. A factor known to impact on patient satisfaction with a prescribed treatment is the route of administration. Here, several studies point to a preference for oral therapies, also among second-line DMARDs.[16,17]

Recently, Tofacitinib, an orally applied DMARD of the new class called Janus-Kinase-Inhibitors (JAK-Inhibitors) has been brought into the market in the European Union. Tofacitinib is indicated in combination with methotrexate (MTX) for the treatment of moderate to severe active rheumatoid arthritis (RA) in adult patients who have responded inadequately to, or who are intolerant to one or more DMARD. Due to oral administration of Tofacitinib, the impact of patient’s satisfaction with drug treatment on therapy decisions by rheumatologists may be especially pronounced.

EULAR recommendations have now endorsed individual patient related factors such as patient preferences and comorbidities as an overarching principle in the management of RA.

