7. RESEARCH METHODS

7.1. Study design

This is a 60-month, prospective, non-interventional, multi-centre study to evaluate the impact of the following factors on the number of treatment escalations of Tofacitinib patients in 24 months.

[figure not shown]
Eligible patients will be followed up from the date of first Tofacitinib prescription for 24 months. Patients who are switched from the initial Tofacitinib therapy to other therapies will also be followed up to 24 months. Patient documentation is expected quarterly as per standard clinical practice.

This study observes drug prescription and follow-up visits in daily medical care. Therapeutic strategies and frequency of patient follow-up are decided by the treating physician.

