7.3. Variables

Variable	Role	Data source(s)	Operational definition
RA-treatment with Tofacitinib and/or other DMARDs - date of initiation	Exposure, Potential confounder, subgroup identifier	Case records and electronic Case Report Form (eCRF)	Details will be provided in Statistical Analysis Plan
RA treatment with Tofacitinib and/or other DMARDs – dose	Exposure, Potential confounder, subgroup identifier	Case records/eCRF	Details will be provided in Statistical Analysis Plan
RA treatment with Tofacitinib and/or other DMARDs - tolerability	Potential confounder, subgroup identifier	Case record/eCRF	Details will be provided in Statistical Analysis Plan
RA treatment with Tofacitinib and/or other DMARDs – route of administration	Potential confounder, subgroup identifier	Case record/eCRF	Details will be provided in Statistical Analysis Plan
Age	Baseline characteristic, potential confounder, sub-group identifier	Case records/eCRF	Details will be provided in Statistical Analysis Plan
Gender	Baseline characteristic, potential confounder, sub-group identifier	Case records/eCRF	Details will be provided in Statistical Analysis Plan
Height	Baseline characteristic, potential confounder, sub-group identifier	Case records/eCRF	Details will be provided in Statistical Analysis Plan
Weight	Baseline characteristic, potential confounder, sub-group identifier	Case records/eCRF	Details will be provided in Statistical Analysis Plan
Insurance Type	Baseline characteristic, Potential confounder, subgroup identifier	Case records/eCRF	Details will be provided in Statistical Analysis Plan
Date of first Diagnosis of RA	Baseline characteristic, potential confounder, sub-group identifier	Case records/eCRF	Details will be provided in Statistical Analysis Plan

Tofacitinib citrate

A3921302 OBSERVATIONAL PLAN NON-INTERVENTIONAL STUDY

Final, 23 August 2017

Smoking history and current smoking status	Baseline characteristic, potential confounder, sub-group identifier	Case records/eCRF	Details will be provided in Statistical Analysis Plan
Comorbidities	Baseline characteristic, potential confounder, sub-group identifier	Case records/eCRF	Details will be provided in Statistical Analysis Plan
Erythrocyte Sedimentation Rate (ESR) and C-Reactive Protein (CRP)	Baseline characteristics and outcome variable	Case records/eCRF	Details will be provided in Statistical Analysis Plan

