7.6.5. Treatment of Rheumatoid Arthritis (RA-Treatment) with Tofacitinib and/or other DMARDs

At each visit (visits 1-9) dose and route of administration (if applicable) of treatment with Tofacitinib and/or other DMARDs will be documented. If an escalation (as defined in section 6.1.1) occurred since the last visit, in addition stop date of previous DMARD(s), start date of new DMARD(s) and reason for switch (lack of efficacy or intolerance) will be documented.

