6.2 FULL ANALYSIS SET

The Full Analysis Set (FAS) will include all patients who receive at least one dose of tofacitinib and have at least one post-baseline visit. The primary analysis will use the FAS. The FAS will include all data collected during the study, both scheduled and unscheduled visits.

The protocol states that patients will be enrolled if they fulfil all selection criteria for the study and are started on treatment with tofacitinib for moderate to severely active rheumatoid arthritis.

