12.1.2 DEFINITION OF TREATMENT ESCALATIONS

Table 11.2 provides an overview of all possible treatment switch combinations relevant for the analysis of the primary endpoint and defines the type of escalations, e.g., whether the treatment switch relates to a step-up, step-down or termination.

Table 12.2: Definition of treatment escalations

Therapy*	Mono Tofa	Mono tsDMARD	Mono csDMARD	MonoTNFi	Mono bDMARD	Combo+ csDMARD	Combo tsDMARD +csDMARD	ComboTNFi +csDMARD	Combo bDMARD+ csDMARD	Therapy Stop
MonoTofa	-	Step-up		Step-down	Step-up	Step-up	Step-up	Step-up	Step-up	Treatment termination
Mono tsDMARD	Step-up	Step-up if different tsDMARD		Step-down	Step-up	Step-up	Step-up	Step-up	Step-up	Treatment termination
Mono csDMARD	Step-up	Step-up	Step-up if different csDMARD		Step-up	Step-up	Step-up	Step-up	Step-up	Treatment termination
MonoTNFi	Step-up	Step-up		Step-down	Step-up if different TNFi	Step-up	Step-up	Step-up	Step-up	Treatment termination
Mono bDMARD	Step-up	Step-up		Step-down	Step-up	Step-up if different bDMARD	Step-up	Step-up	Step-up	Treatment termination
Combo+ csDMARD	Step- down	Step-up		Step-down	Step-up	Step-up	Step-up if different csDMARD	Step-up	Step-up	Treatment termination
Combo tsDMARD +csDMARD	Step-up	Step-up if different tsDMARD; Step-down otherwise		Step-down	Step-up	Step-up	Step-up if different tsDMARD or csDMARD	Step-up	Step-up	Treatment termination
Combo TNFi + csDMARD	Step-up	Step-up		Step-down	Step-down, if same TNFi, Step-up if different TNFi	Step-up	Step-up	Step-up if different csDMARD/TN Fi	Step-up if different bDMARD or csDMARD	Treatment termination
Combo bDMARD+ csDMARD	Step up	Step up		Step down	Step up	Step down if same bDMARD; Step-up otherwise	Step up	Step up	Step up	Step up if different bDMARD or csDMARD
*) Definitions:			Mono tsDMARD= Monotherapy any tsDMARD other than Tofa Mono csDMARD= Monotherapy any csDMARD Mono TNFi= Monotherapy any TNFi Mono bDMARD= Monotherapy any bDMARD other than TNFi Combo Tofa= Combination therapy tofacitinib with any csDMARD Combo csDMARD= Combination therapy tofacitinib + any csDMARD				Combo tsDMARD + csDMARD= Combination therapy tsDMARD other than tofacitinib + any csDMARD Combo TNFi + csDMARD= Combination therapy any TNFi+ any csDMARD Combo bDMARD + csDMARD= Combination therapy bDMARD other than TNFi+ anycsDMARD			

PPD

PPD

PPD

LEGAL DISCLOSURE

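### The primary model pools decisions made on tofacitinib with decisions made after a switch and has no regimen or route term, so its satisfaction hazard ratio is not specific to tofacitinib

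*SAP*

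**What the plan says.** **Who is analysed.** Protocol 7.1 keeps switched patients in follow-up: "Patients who are switched from the initial Tofacitinib therapy to other therapies will also be followed up to 24 months". SAP 6.2 makes the FAS the primary set, without regard to current treatment: "The FAS will include all data collected during the study, both scheduled and unscheduled visits". SAP 9.1.1 describes a recurrent-event Cox model: "This involves fitting either the Andersen and Gill or Prentice, Williams and Peterson gap-time models to the data". That choice is left open, and no order-specific or regimen-specific coefficients are mentioned. The escalation table in SAP 12.1.2 has rows for switches that start from regimens without tofacitinib; one row label is defined as "Mono TNFi= Monotherapy any TNFi". Only the secondary analyses are confined to time on tofacitinib (SAP 9.1.6, 9.2.3).

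**What is adjusted for.** SAP 7.3.3: "A number of potential confounders will also be included in the primary analysis and all sensitivity analyses". The list, repeated in SAP 9.2.6, has ten patient and treatment items and six comorbidities. A closing sentence allows further confounders to be looked into if they emerge. It names none.

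**What the protocol says about route.** Section 5: "A factor known to impact on patient satisfaction with a prescribed treatment is the route of administration". The same section expects that oral dosing may make the influence of satisfaction on decisions stronger. The variables table in 7.3 has the row "RA treatment with Tofacitinib and/or other DMARDs – route of administration", with the roles potential confounder and subgroup identifier. Section 7.6.5 says that at each of the nine visits "dose and route of administration (if applicable) of treatment with Tofacitinib and/or other DMARDs will be documented".

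**The concern.** The satisfaction item (Protocol 7.6.16, SAP 7.3.1) asks about whatever arthritis drugs the patient has had since the previous visit. Before a switch the answer rates tofacitinib, alone or with a partner. Afterwards it may rate another drug given by another route. The primary model treats both answers as the same covariate with one coefficient.

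Two things can then go wrong. If satisfaction weighs differently in decisions on different drugs, the single hazard ratio is an average that may describe none of them. If regimen is related both to satisfaction and to the chance of an escalation, part of the coefficient is confounding by regimen. Either way, a report that uses the primary result to support the oral-treatment argument of Protocol 5 would go beyond what the model can show.

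**Working it through.** **1. The plan's own figures.** None exists for satisfaction: the simulation in Protocol 7.7 has five factors, and satisfaction is not among them. The only power figures given for a named single factor, around 50% at 1500 patients and 60% at 2000 for DAS28 ≤ 3.2, were not reproduced. Schoenfeld's formula with recurrent events gives 90% or more at 1500. Worked backwards (coefficient −0.288, prevalence 0.2, two-sided 5% assumed), 50% power needs 1.96² / (0.2 × 0.8 × 0.288²) = 3.84 / 0.01327 ≈ 290 events, or 290 / 1500 = 0.19 per patient. That mismatch is a separate matter. Here 0.19 serves only as the low end for the event rate.

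**2. Does a listed term stand in for current regimen?**

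| Term in SAP 7.3.3 | Why it does not |
|---|---|
| Tofacitinib dose indicator | Separates two tofacitinib dosing levels; no value defined once the patient is off the drug |
| MTX or partner dose indicator | 1 only for an increase since the last visit, so monotherapy and stable combination are both 0 |
| 2nd or 3rd line | Describes treatment before enrolment |
| Tolerability and efficacy indicators | Give the reason for a termination, not the drug in use |

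**3. Does regimen change which events can occur?** SAP 7.1.1 gives a move from combination to monotherapy as an example of a step-down. In Table 12.2 the move from tofacitinib plus csDMARD to tofacitinib alone is a step-down. A patient on tofacitinib alone cannot make that move; for that patient the only step-down appears to be to csDMARD monotherapy. Several cells are displaced by one column in the extracted text, so this second reading is a reconstruction: the 'if different' entries fall on the diagonal only after shifting back. SAP 9.1.1 fits a model for each escalation type, so the step-down model has risk sets whose members face different possible events.

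**4. How many events could follow an earlier one?** For a homogeneous Poisson count with mean μ, the share that are second or later is 1 − (1 − e^−μ)/μ.

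- μ = 3.16 (planning baseline): 1 − 0.958/3.16 = 70%
- printed coefficients applied (about 4.0 events per patient): 82%, by simulation
- signs of the three VAS coefficients reversed (about 0.65 per patient): 46%, by simulation
- μ = 0.19: 1 − 0.173/0.19 = 9%

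These are not shares of events off tofacitinib, because adding or dropping a csDMARD while staying on tofacitinib also counts.

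**5. What could pooling do to the hazard ratio?** All inputs here are assumptions. The simulation used 60,000 patients, eight quarterly intervals and a complementary log-log analogue of the Andersen-Gill model. Where satisfaction matters, its coefficient is −0.4 per point (hazard ratio e^−0.4 = 0.67). In A to C, other drugs raise the log hazard by 0.4 and non-oral drugs lower satisfaction by 0.5 point; in D these are 0.7 and 1 point.

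| Scenario | Events per patient | Share off tofacitinib | Pooled | Regimen main effect added | Tofacitinib time only |
|---|---|---|---|---|---|
| A. 0.67 on every drug | 1.02 | 35% | 0.645 | 0.668 | 0.668 |
| B1. 0.67 on tofacitinib, 1.0 elsewhere | 0.24 | 10% | 0.688 | 0.693 | 0.666 |
| B2. As B1 | 0.97 | 31% | 0.739 | 0.757 | 0.666 |
| B3. As B1 | 2.67 | 57% | 0.809 | 0.842 | 0.671 |
| C. 1.0 on tofacitinib, 0.67 elsewhere | 1.03 | 33% | 0.862 | 0.882 | 1.006 |
| D. 1.0 on every drug | 1.10 | 37% | 0.929 | 0.998 | 1.002 |

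**6. Hand check.** With a regimen main effect and one satisfaction coefficient, the log hazard ratio should be near the event-weighted mean of the two true values.

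- B1: 0.90 × (−0.4) = −0.360, hazard ratio 0.70
- B2: 0.69 × (−0.4) = −0.276, hazard ratio 0.76
- B3: 0.43 × (−0.4) = −0.172, hazard ratio 0.84
- C: 0.33 × (−0.4) = −0.132, hazard ratio 0.88

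These match the main-effect column to within 0.01. So a main effect removes confounding by regimen (A and D) but still returns an average when effects differ (B and C).

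**The case against.** The strongest reply is that pooling is intended. The title, the objective (Protocol 6) and the primary endpoint (Protocol 6.1.1) concern treatment decisions in patients who start tofacitinib, and follow-up after a switch is deliberate. A reader might infer that the study therefore fails to answer its own question. The documents do not support that: for the broad question the pooled analysis is legitimate, and the tofacitinib-specific expectation appears only in the background section.

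A reader might also infer that the protocol itself establishes route as a confounder. It does not go that far. Section 5 links route to satisfaction and suggests that oral dosing strengthens the effect of satisfaction, which is effect modification. It does not say that route alters escalation by any other path. Nor is the variables table a promise to adjust: height, weight, insurance type and smoking carry the same label and are not terms in SAP 7.3.3 either.

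Other parts of the plan help somewhat. SAP 9.2.3.11 tabulates satisfaction among patients on tofacitinib at the previous visit, split by stopping or staying, but without adjustment. A Prentice-Williams-Peterson model would stratify by event order, but it is only one of two options and no order-specific coefficients are planned. The clause on further confounders permits a regimen term without pre-specifying one.

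What stands after all this is narrower: there is no regimen adjustment, and no adjusted estimate confined to tofacitinib.

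**Conclusion.** The point holds in limited form, as a cheap improvement. The pooled satisfaction hazard ratio is a mixture over regimens. It serves the broad objective but cannot carry a statement about tofacitinib or oral treatment. The per-type models, step-down above all, are also exposed because regimen affects which events are possible, subject to the reconstruction of Table 12.2.

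The size is unknown. It depends on how much follow-up is spent off tofacitinib, whether satisfaction acts differently there, and how strongly regimen relates to satisfaction and hazard; the documents give none of these. Under the assumed inputs the gap runs from negligible (0.69 pooled against 0.67 on tofacitinib) to material (0.86 against 1.01).

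A reader might infer from the planning baseline that at least (3.16 − 1)/3.16 = 68% of events happen on later drugs. That does not follow. The 3.16 is a baseline rate before covariate effects, so 68% is not a floor (step 4 spans 9% to 82%), and later events can still occur on tofacitinib.

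**What to change.** Keep the pooled FAS analysis for the broad objective, and amend the SAP in three places.

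1. In 7.3.3, add time-varying terms taken at the start of each interval, so that they precede the event: current regimen (tofacitinib versus other DMARD, or route if the two are collinear) and monotherapy versus combination. State how the tofacitinib dose indicator is coded once a patient is off the drug.
2. In 9.2.2, pre-specify a supportive analysis limited to intervals on tofacitinib, with the first departure counted as an event and the patient censored afterwards, or else a satisfaction-by-on-tofacitinib interaction. SAP 6.3 already defines being on tofacitinib; state how pauses are handled. A main effect alone is not enough, as scenarios B and C show.
3. State that only the analysis in item 2 supports statements specific to tofacitinib.

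Regimen and route are recorded at every visit, so no new data are needed. The model now has six factors and sixteen confounder terms (ten items plus six comorbidities); this adds two, or three with the interaction. The price is slightly wider intervals and some collinearity, which the collinearity check already planned in 9.2.2 can cover.
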